1.3. Schedule of Activities (SoA)

Table 1 Time and Events Table

Procedure	Pre- Screen	Screenin g	Treatment Period (visit window is ± 7days)			IP Discontinu ation visit	End of study visit	Notes			
Visit		1	2	3	4	5	6	7		8	
Week		-2 to -1	0	4	8	12	16	20	4 weeks post last dose ± 7 days	24 or Early Withd rawal	
Written Informed Consent	X	X									 Pre-screen visit can occur on the same day as the Visit 1 but must be completed prior to starting Visit 1 (screening) procedures. Visit 2 (Week 0) must occur at least one week following Visit 1 (screening) Visit 2 (Week 0) will be considered Baseline
Demography		X								:	
Medical History		X									
Asthma and Exacerbation History (including triggers)		Х									
Asthma Therapy History		X									Therapy history to include a detailed review of prior monoclonal antibodies received for treatment of asthma, including prior investigational anti-IL5 or anti-IL13 preparations.

Procedure	Pre- Screen	Screenin g		Treatment Period (visit window is ± 7days)			IP Discontinu ation visit	End of study visit	Notes		
Visit		1	2	3	4	5	6	7		8	
Week		-2 to -1	0	4	8	12	16	20	4 weeks post last dose ± 7 days	24 or Early Withd rawal	
Oral Corticosteroid Therapy History		X									
Smoking History		X									
Cardiovascular History/risk factors		X									
Parasitic Screening		X									
Inclusion/Exclusion Criteria		х	х								Study inclusion/exclusion criteria should be reviewed at the beginning of visit 2(Week 0). The review should include the results of any lab/safety assessments conducted at Visit 1 (screening).
Treatment Period Criteria			x								
Efficacy Assessments						_		_			
Exacerbation review			х	X	X	х	х	х	X	Х	Number of clinically significant exacerbations (including exacerbations requiring hospitalization, Emergency Department) visits will be evaluated
Spirometry including FEV ₁ , FVC		Х	х		Х		Х		X	Х	

Procedure	Pre- Screen	Screenin g	Treatment l		7days)				IP Discontinu	End of study	Notes
									ation visit	visit	
Visit		1	2	3	4	5	6	7		8	
Week		-2 to -1	0	4	8	12	16	20	4 weeks post last dose ± 7 days	24 or Early Withd rawal	
Maximum Post Bronchodilator Procedure		х	x						х	X	Maximum Post Bronchodilator Procedure is required to complete reversibility testing. If participant does not reverse ≥12% in FEV₁ at Visit 1 (screening), the procedure may be repeated at Visit 2 (Week 0).
OCS dose adjustment review (where applicable)		Х		х	Х	Х	Х	Х			OCS dose adjustment should be reviewed at scheduled in-clinic Visits

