10.6. Appendix 6: Liver Safety: Required Actions and Follow-up Assessments

Phase III-IV liver chemistry stopping and increased monitoring criteria have been designed to assure participant safety and evaluate liver event aetiology

Phase III-IV liver chemistry stopping criteria and required follow up assessments

Liver Chemistry Stopping Criteria				
ALT-absolute	ALT ≥ 8Xuln			
ALT Increase	ALT $\geq 5x$ ULN but $<8x$ ULN persists for ≥ 2 weeks ALT $\geq 3x$ ULN but $<5x$ ULN persists for ≥ 4 weeks			
Bilirubin ^{1, 2}	ALT $\geq 3x$ ULN and bilirubin $\geq 2x$ ULN (>35% direct bilirubin)			
INR ²	ALT ≥ 3xULN and INR>1.5			
Cannot Monitor	ALT ≥ 5xULN but <8xULN and cannot be monitored weekly for ≥2 weeks ALT ≥ 3xULN but <5xULN and cannot be monitored weekly for ≥4 weeks			
Symptomatic ³	ALT \geq 3xULN associated with symptoms (new or worsening) believed to be related to liver injury or hypersensitivity			
Required Action	ons and Follow up Assessmen	ts		
Actions		Follow Up Assessments		
 Immediately discontinue study intervention Report the event to GSK within 24 hours Complete the liver event CRF and complete an SAE data collection tool if the event also meets the criteria for an SAE² 		 Viral hepatitis serology⁴ Obtain INR and recheck with each liver chemistry assessment until the transaminases values show downward trend Only in those with underlying chronic Hepatitis B at study entry (identified by positive Hepatitis B surface antigen) quantitative Hepatitis B 		
assessmentsMonitor tl	ne participant until liver resolve, stabilize, or return to	 DNA and Hepatitis delta antibody⁵. Serum creatine phosphokinase (CPK) and lactate dehydrogenase (LDH). Fractionate bilirubin, if total 		

Liver Chemistry Stopping Criteria

MONITORING below)

- Do not restart/rechallenge participant with study treatment unless allowed per protocol and GSK Medical Governance approval is granted (refer to Appendix 6)
- If restart/rechallenge **not allowed or not granted**, permanently discontinue study intervention and continue participant in the study for any protocol specified follow up assessments

MONITORING:

For bilirubin or INR criteria:

- Repeat liver chemistries (include ALT, AST, alkaline phosphatase, bilirubin and INR) and perform liver event follow up assessments within 24 hrs
- Monitor participants twice weekly until liver chemistries resolve, stabilize or return to within baseline i.e. Visit 3
- A specialist or hepatology consultation is recommended

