For All other criteria:

- Repeat liver chemistries (include ALT, AST, alkaline phosphatase, bilirubin and INR) and perform liver event follow up assessments within 24-72 hrs
- Monitor participants weekly until liver chemistries resolve, stabilize or return to within baseline i.e. Visit 3

bilirubin≥2xULN

- Obtain complete blood count with differential to assess eosinophilia
- Record the appearance or worsening of clinical symptoms of liver injury, or hypersensitivity, on the AE report form
- Record use of concomitant medications on the concomitant medications report form including acetaminophen, herbal remedies, other over the counter medications.
- Record alcohol use on the liver event alcohol intake case report form (CRF) page

For bilirubin or INR criteria:

- Anti-nuclear antibody, anti-smooth muscle antibody, Type 1 anti-liver kidney microsomal antibodies, and quantitative total immunoglobulin G (IgG) or gamma globulins.
- Serum acetaminophen adduct high performance liquid chromatography (HPLC) assay (quantifies potential acetaminophen contribution to liver injury in participants with definite or likely acetaminophen use in the preceding week [James, 2009]).
- Liver imaging (ultrasound, magnetic resonance, or computerised tomography) and /or liver biopsy to evaluate liver disease; complete Liver Imaging and/or Liver Biopsy CRF forms.
- 1. Serum bilirubin fractionation should be performed if testing is available. If serum bilirubin fractionation is not immediately available, discontinue study intervention for that participant if ALT ≥ 3xULN and bilirubin ≥ 2xULN. Additionally, if serum bilirubin fractionation testing is unavailable, record presence of detectable urinary bilirubin on dipstick, indicating direct bilirubin elevations and suggesting liver injury.

- 2. All events of ALT \geq 3xULN and bilirubin \geq 2xULN (>35% direct bilirubin) or ALT \geq 3xULN and INR>1.5 which may indicate severe liver injury (possible 'Hy's Law'), must be reported as an SAE (excluding studies of hepatic impairment or cirrhosis); the threshold value stated will not apply to participants receiving anticoagulants
- 3. New or worsening symptoms believed to be related to liver injury (such as fatigue, nausea, vomiting, right upper quadrant pain or tenderness, or jaundice) or believed to be related to hypersensitivity (such as fever, rash or eosinophilia)

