- 4. Includes: Hepatitis A immunoglobulin M (IgM) antibody; HBsAg and HBcAb; hepatitis C RNA; cytomegalovirus IgM antibody; Epstein-Barr viral capsid antigen IgM antibody (or if unavailable, heterophile antibody or monospot testing); and hepatitis E IgM antibody.
- 5. If hepatitis delta antibody assay cannot be performed, it can be replaced with a polymerase chain reaction (PCR) of hepatitis D RNA virus (where needed) [Le Gal, 2005].

Phase III-IV liver chemistry increased monitoring criteria with continued therapy

Liver Chemistry Increased Monitoring Criteria – Liver Monitoring Event				
Criteria	Actions			
ALT ≥5xULN and <8xULN and bilirubin <2xULN without symptoms believed to be related to liver injury or hypersensitivity, and who can be monitored weekly for 2 weeks. OR ALT ≥3xULN and <5xULN and bilirubin <2xULN without symptoms believed to be related to liver injury or hypersensitivity, and who can be monitored weekly for 4 weeks.	 Notify the GSK medical monitor within 24 hours of learning of the abnormality to discuss participant safety. Participant can continue study intervention. Participant must return weekly for repeat liver chemistries (ALT, AST, alkaline phosphatase, bilirubin) until they resolve, stabilise or return to within baseline i.e. Visit 3 If at any time participant meets the liver chemistry stopping criteria, proceed as described above If ALT decreases from ALT ≥5xULN and <8xULN to ≥3xULN but <5xULN, continue to monitor liver chemistries weekly. If, after 4 weeks of monitoring, ALT <3xULN and bilirubin <2xULN, monitor participants twice monthly until liver chemistries normalize or return to within baseline i.e. Visit 3. 			

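### Appendix 6 names Visit 3 (Week 4, on drug) as the liver-chemistry baseline in four places, against Visit 2 in the Schedule of Activities; a minor error that bears mainly on the twice-monthly step-down rule

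*Protocol*

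**What the plan says.** The Schedule of Activities (Protocol 1.3) fixes the reference visit: "Visit 2 (Week 0) will be considered Baseline". The first dose is given at that visit (Protocol 4.1.2). Visit 3 is Week 4 (Protocol 1.3; SAP visit-window table).

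Protocol Appendix 6 (Section 10.6) uses a different visit in each of its four follow-up rules:

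- Stopping criteria, bilirubin or INR: "Monitor participants twice weekly until liver chemistries resolve, stabilize or return to within baseline i.e. Visit 3".
- Stopping criteria, all others: "Monitor participants weekly until liver chemistries resolve, stabilize or return to within baseline i.e. Visit 3".
- Increased monitoring with therapy continued, weekly phase: "Participant must return weekly for repeat liver chemistries (ALT, AST, alkaline phosphatase, bilirubin", with the closing bracket, then "until they resolve, stabilise or return to within baseline i.e. Visit 3".
- Increased monitoring with therapy continued, step-down phase: the entry condition is "If, after 4 weeks of monitoring, ALT <3xULN and bilirubin <2xULN", and sites are then to "monitor participants twice monthly until liver chemistries normalize or return to within baseline i.e. Visit 3".

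The last two rules apply where "Participant can continue study intervention".

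**The concern.** A baseline used to judge recovery from a possible drug-related liver event should come from before the drug. By Visit 3 the participant has had one dose and about four weeks of exposure. If chemistries had already risen by then, the Visit 3 value sets the recovery target too high, and a site that follows the text literally could end follow-up at a level the participant did not have before treatment. These are working instructions to sites, in a trial whose primary objective is safety, and two of the four rules concern participants who are still being dosed.

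**Working it through.** There is no planned figure to reproduce. The check compares the texts and then sizes the monitoring that could be lost.

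**1. Is any post-dose baseline intended?** No section gives a reason for one. SAP 7.2.2 names another visit again (Visit 1), but that is also pre-dose; the difference between Visits 1 and 2 is a separate matter. Chemistry is scheduled at Visit 2 (Protocol 1.3; SAP 11.3), so a pre-dose value is available.

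**2. Where does the label decide anything?** Three of the four rules can also end on resolution or stabilisation, so the baseline exit will rarely be the one that counts. The step-down rule has only two exits, normalisation or return to baseline. Protocol 5.3 admits participants with ALT up to 2 x ULN. Someone who entered above ULN may never normalise, and the baseline exit then decides.

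**3. At what ALT could the step-down end too early?** Work in multiples of ULN and take normal as 1. The step-down starts only below 3.

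- End point as written = max(1, Visit 3 ALT).
- End point with the correct visit = max(1, Visit 2 ALT).

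| Visit 2 (assumed) | Visit 3 (assumed) | ALT range in which draws could end early |
|---|---|---|
| 1 | 2.5, event later | 1 to 2.5 |
| 2 | 2.5, event later | 2 to 2.5 |
| 1 | 4, event found at Visit 3 | 1 to <3 |
| 2 | 4, event found at Visit 3 | 2 to <3 |

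All these values are illustrative. That includes the Visit 2 value of 2: Protocol 5.3 sets the limit without naming a visit, and Visit 2 chemistry is a separate draw. AST, alkaline phosphatase and bilirubin must also be normal or back to their Visit 3 values. If Visit 3 values are at or below Visit 2, nothing is lost.

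The last two rows show a further oddity. When the event is found at Visit 3, the event value itself becomes the baseline under all four rules. For an event between Visits 2 and 3, no Visit 3 value exists yet and the baseline exit cannot be used.

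**4. How many draws?** Assume that twice monthly means every 2 weeks. For an event at Week E, weekly draws run to E+4, and step-down draws then fall at E+6, E+8 and so on up to Week 24. Chemistry is scheduled at Weeks 4, 8, 12, 16, 20 and 24 in any case.

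| Event week | Step-down draws | Unscheduled, so can be lost |
|---|---|---|
| 4 | 10, 12, 14, 16, 18, 20, 22, 24 (8) | 10, 14, 18, 22 (4) |
| 8 | 14, 16, 18, 20, 22, 24 (6) | 14, 18, 22 (3) |
| 12 | 18, 20, 22, 24 (4) | 18, 22 (2) |
| 16 | 22, 24 (2) | 22 (1) |
| 20 | none | 0 |
| 5 (unscheduled sample) | 11, 13, 15, 17, 19, 21, 23 (7) | all 7 |

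Each count assumes that the participant neither normalises nor returns to Visit 2 values before Week 24. Protocol Section 8 allows unscheduled safety samples, so the Week 5 case is possible and the 4 from scheduled visits is not an overall maximum.

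**The case against.** The case for leaving this alone is that the label hardly ever bites. For the step-down rule to end early, a participant needs an asymptomatic ALT event of 3 to <8 x ULN with bilirubin below 2 x ULN, a fall below 3 x ULN by four weeks, failure to normalise, Visit 3 values above both normal and Visit 2, and the other analytes meeting the exit as well. The widest ranges and the 4-draw count come from an event found at Visit 3, where treating the event value as baseline is a strained reading. An investigator who has had to notify the medical monitor is unlikely to adopt it.

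Other safeguards also stand. Weekly draws over the 2- or 4-week window are enforced by the continued-therapy criteria and by the stopping rule for participants who cannot be monitored. Chemistry continues every 4 weeks. Protocol 8.2.6 separately requires clinically significant values to be repeated until normal, back to baseline or no longer judged significant, and it names no visit; since it sets no interval, it covers the gap only in part.

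All of this holds, and it settles the severity. It does not supply a reason for Visit 3, and it leaves sites with two retest rules that can point to different reference values.

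A reader might infer more: that participants could be kept on drug past a stopping threshold, or that the primary safety result is compromised. The documents do not support either. Stopping, increased-monitoring and entry thresholds are multiples of ULN and do not use baseline, and the adverse-event incidence estimand does not refer to it.

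**Conclusion.** The inconsistency is certain: four statements in current, operative text contradict the Schedule of Activities and place the baseline after the first dose. The consequence is minor. It is a loss of monitoring frequency, from about every 2 weeks to every 4, in participants who reach the step-down rule with raised Visit 3 values. For events found at scheduled visits the loss is 0 to 4 unscheduled draws per affected participant; for events found at unscheduled samples it can be larger, 7 in the Week 5 example. No overall maximum should be quoted.

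These counts rest on a 2-week reading of twice monthly and on no earlier recovery. The ALT ranges rest on assumed Visit 2 and Visit 3 values. The documents give no liver-event rate, so the number affected cannot be estimated; given how many conditions must coincide, few are expected. The label may be a remnant of an earlier visit schedule, but the documents do not say so and nothing here depends on it.

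**What to change.** Replace Visit 3 with Visit 2 (Week 0, pre-dose) at all four places in Appendix 6: the two monitoring rules under the stopping criteria, and the weekly and step-down rules under increased monitoring. Do this by protocol amendment, or by a written clarification to sites followed by an amendment, so that sites need not wait for the amendment and its ethics approval (Protocol 10.1.1).

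The Visit 2 sample is already scheduled, so no new baseline draw is needed. The cost is four phrases of text and some additional twice-monthly draws in the few participants who would otherwise have stopped against a raised Visit 3 value.

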10.7. Appendix 7: Anaphylaxis Criteria

Hypersensitivity reactions will be monitored using the diagnostic criteria for anaphylaxis as outlined by the Joint NIAID/FAAN Second Symposium on Anaphylaxis [Sampson, 2006]. The criteria do not make a distinction based on underlying mechanism. These criteria are summarized as follows:

- 1. Acute onset of an illness (minutes to several hours) with involvement of the skin, mucosal tissue, or both (e.g., generalized hives, pruritus or flushing, swollen lips-tongue-uvula), and at least one of the following:
 - a. Respiratory compromise (e.g., dyspnea, wheeze-bronchospasm, stridor, reduced PEF, hypoxemia)
 - b. Reduced BP or associated symptoms of end-organ dysfunction (e.g., hypotonia [collapse], syncope, incontinence)
- 1. Two or more of the following that occur rapidly after exposure to a likely allergen for that patient (minutes to several hours):
 - a. Involvement of the skin-mucosal tissue (e.g., generalized hives, itch-flush, swollen lips-tongue-uvula)
 - b. Respiratory compromise (e.g., dyspnoea, wheeze-bronchospasm, stridor, reduced PEF, hypoxemia)
 - c. Reduced BP or associated symptoms (e.g., hypotonia [collapse], syncope, incontinence)
 - d. Persistent gastrointestinal symptoms (e.g., crampy abdominal pain, vomiting)
- 2. Reduced BP after exposure to known allergen for that patient (minutes to several hours):
 - a. Infants and children: low systolic BP (age specific) or greater than 30% decrease in systolic BP
 - b. Adults: systolic BP of less than 90 mm Hg or greater than 30% decrease from that person's baseline

10.8. Appendix 8 : Daily Asthma Symptom Score

10.9. Appendix 9 - Criteria for e-Diary Alerts Indicative of a Potential Asthma Worsening

Criteria ¹	Definition
1	Mean AM PEF <80% of baseline stability limit
2	Mean asthma-related night time awakenings >50% increase over the baseline
	period (per night), >150% of the baseline mean
3	Rescue medication use requiring 4 or more puffs/day above the mean baseline
	value for any 2 consecutive days in the prior week, or 12 puffs or more on
	any one day in the prior week
4	Change in ACQ-5 \geq +0.5 from the prior month OCS dose assessment
5	Symptoms of adrenal insufficiency

^{1.} Baseline means for AM PEF, night time awakenings, and rescue medication use are calculated on a per night or per day basis using participant diary information from the 7 days prior to Visit 2

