4.1.1. Screening

Participants who meet all eligibility criteria at the Screening visit (Visit 1) will enter the study and asked to come to the clinic after at least 1 week for Visit 2 (Week 0).

Participants must understand and agree to use the study drugs for the treatment of asthma, or asthma exacerbation, for the duration of the study. OCS use and OCS dose adjustment in participants will be as per the investigator's discretion and clinical practice.

At Visit 1, the screening visit, the screening ACQ-5 score will be captured. Participants who meet study eligibility criteria, are eligible to enter the Treatment period. All screening procedures will be performed -2 weeks to -1 week (screening visit would be at least 7 day prior to dosing visit) before first dose of mepolizumab (Visit 2, Week 0).

The ACQ-5 questionnaire has been validated in several separate studies and the minimal clinically important difference value of +0.5 has been established to demonstrate a significant clinical change in asthma status (Juniper, 1999; Korn, 2011).

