5.1. Inclusion Criteria

Participants are eligible to be included in the study only if all of the following criteria apply:

Age

1. Participant must be ≥ 18 to 65 years of age inclusive, at the time of signing the informed consent.

Type of Participant and Disease Characteristics

- 2. Asthma: Evidence of asthma as documented by either:
 - Airway reversibility (FEV1≥12% and 200 ml) demonstrated at Visit 1 (screening), or Visit 2 (Week 0) OR documented in the previous 12 months OR
 - Airway hyper-responsiveness (methacholine: PC20 of <8mg/mL or histamine: PD20 of $<7.8~\mu$ mol; mannitol: decrease in FEV1 as per the labelled product instructions) documented in the 12 months prior to Visit 2 (Week 0) OR
 - Airflow variability in clinic FEV1 ≥20% between two consecutive clinic visits documented in the 12 months prior to Visit 2 (FEV1 recorded during an exacerbation should not be considered for this criteria) OR
 - Airflow variability as indicated by >20% diurnal variability in peak flow observed on 3 or more days during the optimisation period
- 3. Participants with Eosinophilic asthma: prior documentation of eosinophilic asthma or high likelihood of eosinophilic asthma as
 - FEV1: Persistent airflow obstruction as indicated by:
 - For participants \geq 18 years of age at Visit 1 (screening), or Visit 2 (Week 0), a prebronchodilator FEV1 <80% predicted
 - For predicted FEV1 values NHANES III values will be used and adjustments to these values will be made for race [Hankinson, 1999].
- 4. Eosinophilic Phenotype: Airway inflammation characterized as eosinophilic in nature as indicated by one of the following characteristics:
 - a. An elevated peripheral blood eosinophil level of ≥300 cells/µL that is related to asthma within the previous 12 months prior to Visit 2 (Week 0)

OR

b. Peripheral baseline eosinophil level ≥150 cells/μL between Visit 1 (screening) and Visit 2 (Week 0) that is related to asthma

- 5. Patients eligible for mepolizumab treatment as per independent clinical judgment of treating physician in alignment with local prescribing information.
- 6. Inhaled Corticosteroids: requirement for regular treatment with high dose inhaled corticosteroid in the 6 months prior to Visit 1 (screening).

For 18 years of age and older:

- ICS dose must be ≥880 mcg/day fluticasone propionate (FP) (ex-actuator) or equivalent daily.

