For safety reasons alerts will be programmed into the eDiary to encourage the participant to contact the investigator if their asthma worsens (see Appendix 9). However, an alert in itself will not be classified as a clinically significant exacerbation.

8.1.3. Pulmonary Function Testing including Reversibility using the Maximum Post-Bronchodilator Method

Spirometry will be conducted, using the Spirometry equipment provided by GSK through a designated central laboratory at the visits specified in the Time and Events schedule. The spirometer should meet American Thoracic Society standards and produce a printout of all data generated, which should be stored in the participant's notes. The spirometer should be calibrated in accordance with the manufacturer's instructions and a calibration log maintained. Participants should withhold short-acting beta-2-agonists (SABAs) for ≥ 6 hours and LABAs for ≥ 12 hours prior to clinic visit. Assessments to be recorded will include FEV₁, and FVC.

Pre-bronchodilator measurements will be taken at baseline, week 8, 16, and 24. In addition, at visit specified in the Time and Events schedule, post-bronchodilator values will be recorded following reversibility testing, using the maximum post bronchodilator method. For participants unable to achieve ≥12% reversibility and 200mL change at Visit 1 (screening), reversibility can be repeated at Visit 2 (Week 0). The procedures to achieve the maximum post-bronchodilator are those generated by the Asthma Clinical Research Network. Further details of spirometry and reversibility testing procedures are presented in the SRM.

8.1.4. eDiary

The participant will be asked to record the following parameters daily in the eDiary from Visit 1 (screening) onwards:

- Morning peak flow (best of three), before rescue medication usage (L/min)
- Number of puffs of rescue usage over the previous 24-hours
- Asthma symptom score over the previous 24-hours using a 6-point scale (Appendix 8)
- Frequency of awakening due to asthma symptoms requiring rescue medication use.
 - Daily dose of OCS

The participant will be asked to complete the ACQ-5 weekly in the eDiary from Visit 1 (screening) onwards.

From Visit 1 (screening) to Visit 2 (Week 0) only, participants will record peak flow twice a day to allow for calculation of PEF diurnal variability.

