9.4. Statistical Analyses

All analyses of safety data and efficacy data will be generated for the Safety Population. Additionally separate subgroup analyses will also be generated by with/without baseline maintenance OCS use (with separate summaries in those participants receiving maintenance OCS at baseline and those not maintenance OCS at baseline).

The study Statistical Analysis Plan (SAP) will be finalised prior to database lock which will include a more technical and detailed description of the statistical analyses described in this section. This section is a summary of the planned statistical analyses of the most important primary, secondary and exploratory endpoints.

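### Alert criterion 4 in Protocol Appendix 9 measures ACQ-5 change from an OCS dose assessment, so its reference is undefined as written for participants not taking OCS

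*Protocol*

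**What the plan says.** The alerts are introduced in Protocol Section 8.1.2: "For safety reasons alerts will be programmed into the eDiary to encourage the participant to contact the investigator if their asthma worsens". Nothing there or in Section 8.1.4 limits them to OCS users.

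Appendix 9 gives five criteria. Criterion 4 is a change in ACQ-5 of at least +0.5 "from the prior month OCS dose assessment". Footnote 1 to the same table supplies reference values for three other inputs: "Baseline means for AM PEF, night time awakenings, and rescue medication use are calculated on a per night or per day basis", from the 7 days before Visit 2.

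In the Schedule of Activities (Section 1.3) the nearest procedure is the row "OCS dose adjustment review (where applicable", with the note "OCS dose adjustment should be reviewed at scheduled in-clinic Visits". It is marked at Visit 1 and at Visits 3 to 7.

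On who takes OCS, Section 4.1.1 says "OCS use and OCS dose adjustment in participants will be as per" the investigator's discretion. Inclusion criterion 5 (Section 5.1) carries no OCS requirement: "Patients eligible for mepolizumab treatment as per independent clinical judgment of treating physician in alignment with local prescribing information". Section 9.4 plans separate summaries for "those participants receiving maintenance OCS at baseline and those not maintenance OCS at baseline".

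**The concern.** A threshold on change needs a defined starting value. Criterion 4 takes its starting value from an event tied to OCS dosing, in a protocol that now admits participants who take none. The wording fits the OCS phases that Amendment 4 removed (Appendix 12), but it stands in the current Appendix 9 and is operative text.

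What is at stake is a safety prompt, not an estimate. Section 4.1.1 treats 0.5 on the ACQ-5 as the minimal clinically important difference. If the criterion were programmed exactly as worded, a participant not taking OCS could worsen by that amount without triggering this alert. If the programmer supplied a reference instead, the protocol does not say which one.

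**Working it through.** No arithmetic applies beyond counting, and the plan states no figure to reproduce. The check sets the passages side by side.

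1. **What criterion 4 needs.** A current ACQ-5 score, and an earlier score fixed by an OCS dose assessment in the prior month.

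2. **Is the current score available?** Yes. Section 8.1.4 asks every participant to complete the ACQ-5 weekly in the eDiary from Visit 1.

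3. **Does the reference event exist in the schedule?** Not under that name. The OCS dose adjustment review is marked at Visit 1 and Visits 3, 4, 5, 6 and 7, which is 1 + 5 = 6 of the 8 numbered visits. It is not marked at Visit 2, at Visit 8 or at the IP discontinuation visit. The row is conditional, and the condition is not defined.

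4. **Who has the event?** Under Sections 4.1.1 and 5.1 OCS is neither required nor excluded, and Section 9.4 expects participants both with and without maintenance OCS at baseline. On the natural reading of the condition, a participant taking no OCS has 0 applicable reviews, hence 0 reference points for criterion 4. The affected group is not identical to the planned subgroup, because a participant without maintenance OCS at baseline may receive OCS later.

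5. **Does another passage supply a substitute?**
   - Footnote 1 covers morning PEF, awakenings and rescue use, the inputs to criteria 1 to 3. Those criteria compare with baseline, while criterion 4 compares with the prior month. The absence of ACQ-5 from the footnote is therefore not a second fault, but the footnote does not fill the gap.
   - SAP Appendix 3 defines an ACQ baseline window (study day -7 to day 1) for analysis. It is not an alert rule, and a fixed baseline is not a prior-month value.
   - Sections 8.1.4 and 8.1.5 set the collection of ACQ-5 and name no alert reference.

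6. **What uses the alert?** Sections 8.1.2 and 8.1.4 both say that an alert is not in itself a clinically significant exacerbation. No endpoint, stopping rule or SAP analysis refers to it.

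**The case against.** The strongest reply is that this is a terminology gap that any programmer would bridge. An OCS review is scheduled at most visits, daily OCS dose is an eDiary item for all participants (Section 8.1.4), the ACQ-5 is weekly for all, and visits are four weeks apart. The reference to the prior month could then be read as the ACQ-5 score around the preceding monthly visit.

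Much of this stands. A reader might infer that the current design schedules no OCS assessment at all, or that the alert cannot be computed. The documents support neither: a conditional review is scheduled, the scores exist, and the wording gives a partial time anchor. What is missing is the rule that selects the earlier score for someone to whom the OCS review does not apply. Reading the review as universal would set aside the condition in its own row.

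A second reply is that other safeguards cover the gap. Criteria 1 to 3 do not depend on OCS. Sites view participant data regularly through a web portal and review eDiary data at clinic visits (Section 8.1.4). The schedule marks ACQ-5 review at Visits 1, 2, 5 and 8 and at IP discontinuation, and exacerbation review at every visit from Visit 2. This also stands and keeps the point minor. It does not supply criterion 4 with a reference.

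**Conclusion.** The point holds in a limited form. For participants not taking OCS, criterion 4 has no defined reference as written, and read literally it would not fire for them. This rests on one assumption: that the conditional OCS review is not carried out in participants who take no OCS.

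The size is one of five alert criteria, in a share of participants that the documents do not give. It could be a small part or most of those enrolled under the current protocol.

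A reader might go further and conclude that these participants are unmonitored for worsening, or that the eDiary is actually failing to alert. The documents do not show either. Other alerts and reviews apply to them, and the eDiary specification, which may already contain a workable reference, is not among the documents. Nor is there any effect on the safety or efficacy estimates, since no analysis uses the alert. Severity is minor: worth correcting because it is a live safety rule and the correction is cheap.

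**What to change.** Reconcile Appendix 9 criterion 4 with the current Schedule of Activities, so that the ACQ-5 change is measured from an assessment that every participant has. The sponsor's medical team should choose that reference; none is proposed here. Check the eDiary configuration against the reconciled text, for participants with and without OCS. If dosing has already finished, record in the study file which reference the eDiary used.

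The cost is one line of the protocol and one configuration check. No sample size, endpoint or SAP analysis changes.
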